5.4 Withdrawal of individual subjects

Subjects can leave the study at any time for any reason if they wish to do so, without any consequences. The principal investigators can decide to withdraw a subject from the study for urgent medical reasons.

Reasons to terminate a patient's participation include:

- The patient withdraws her/his consent
- The nature of the patient's treatment is changed to coercive treatment (based on judicial ruling)
- The investigator considers a patient's continued participation in the study to be unjustifiable on medical or psychiatric grounds (i.e., because of side effects or unusual risks of the treatments).

If an individual patient is discontinued due to one of the above-mentioned reasons, this patient will be treated as usual in normal daily practice. The treating physician remains the primary caregiver during the study and will be contacted at the baseline visit and updated throughout the study. The treating physician will contact the study team in cases of important changes and will be responsible to apply for legal custody if appropriate.

All patients leaving the study early, regardless of the reason, will be requested to return to the site for an "early termination" visit to finalize participation. If the patient is not willing to complete all measures, priority will be given to the PCL-5 and OQ-45.

There are no consequences if a patient also refuses this.

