6.2.2. Serious adverse events (SAEs)

We do not expect any serious adverse event (i.e. any untoward medical occurrence or effect that results in death; is life threatening (at the time of the event); requires hospitalisation or prolongation of existing hospitalisation; results in persistent or significant disability or incapacity; is a congenital anomaly or birth defect; any other important medical event that may not result in death, be life threatening, or require hospitalization, may be considered a serious adverse experience when, based upon appropriate medical judgement, the event may jeopardize the subject or may require an intervention to prevent one of the outcomes listed above). The main reason for this is that all four treatments given in the RCTs are evidence-based for at least one of the disorders the patients suffer from (PTSD and PD) and patients who will be assigned to the PTSD-treatment only can given PD-treatment as well after T4 (after 6-12 months) within the research design.

Suicidality or self-injurious behaviour is very common in the study population included for this study. It is also known that starting a new treatment, such as EMDR or DBT could increase symptoms in the beginning, which can develop into suicidal behaviour. SAE's which will occur during the treatment and for which medical care is needed, will be reported to the accredited METC. To monitor the SAE's, patients will be asked to fill in a self-injury questionnaire (*Opzettelijk zelfverwondend gedrag, Baetens & Claes 2014 based on The Brief Non-Suicidal Self-Injury Assessment Tool (BNSSI-AT) van Janis Whitlock en Amanda Purington (2013)*) at the regular assessments. In case of SAE's for which medical care is needed, in between the assessments, therapists will report these incidents to the researchers at the weekly consultations, whom will report these to the accredited METC. The sponsor will report SAEs to the accredited METC that approved the protocol, within 7 days of first knowledge for SAEs that result in death or are life threatening followed by a period of maximum of 8 days to complete the initial preliminary report. All other SAEs will be reported within a period of maximum 15 days after the sponsor has first knowledge of the serious adverse events.

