6.5 Data Safety Monitoring Board

It has been decided not to engage a Data Safety Monitoring Board in this study, no pharmacological or other agents are involved in this study. In addition, no interim analyses are planned. In the investigator's opinion, implementation of a DSMB will not have sufficient added value for the current study.

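### Section 6.2.2 routes SAEs between assessments through weekly therapist consultations, with no faster route for fatal or life-threatening events, and does not say whose first knowledge starts the 7-day clock

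*Combined protocol and SAP*

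**What the plan says.** Section 6.2.2 describes two ways for an SAE to reach the study team. At the regular assessments, "patients will be asked to fill in a self-injury questionnaire". The second route relies on the treatment staff: "therapists will report these incidents to the researchers at the weekly consultations, whom will report these to the accredited METC". Its scope is limited; it applies "In case of SAE's for which medical care is needed, in between the assessments".

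The same section then sets the time limits to the METC. The sponsor reports fatal or life-threatening events "within 7 days of first knowledge for SAEs that result in death or are life threatening" and then has up to 8 more days to finish the preliminary report. For the rest, "All other SAEs will be reported within a period of maximum 15 days after the sponsor has first knowledge of the serious adverse events".

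Two other sections bear on how the team learns of events. Section 5.4 says "The treating physician will contact the study team in cases of important changes". Section 6.2.1 requires adverse events that subjects report, or that the investigator or staff observe, to be recorded. Neither gives a time.

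On oversight, section 6.5 says "It has been decided not to engage a Data Safety Monitoring Board in this study". Section 6.3 marks the annual safety report as not applicable.

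**The concern.** The 7- and 15-day limits govern the last step, from sponsor to METC. The step before it, from therapist to researchers, is tied to a weekly meeting, and nothing shortens it for the gravest events. A therapist who learns of an event just after one consultation can follow the text exactly and mention it a week later.

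This matters more here than in many psychotherapy trials. Section 6.2.2 itself describes suicidal and self-harming behaviour as frequent in these patients, and says that beginning therapy may at first worsen symptoms to the point of suicidal behaviour. Without a DSMB or an annual safety report, the annual progress report (section 9.4) is the only other scheduled summary of SAEs to the committee. Timely outside review, and any suspension under section 6.1, therefore depends largely on individual SAE reports.

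There is also an ambiguity. The 15-day sentence names the sponsor's first knowledge as the start. The 7-day sentence says only first knowledge.

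**Working it through.** The documents give no end-to-end figure to reproduce. The check adds the longest intervals the text allows.

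**Inputs**
- Therapist to researchers: weekly (6.2.2). Assumed longest wait w = 7 days, with no consultation skipped.
- Fatal or life-threatening SAE to METC: 7 days, plus up to 8 to complete the preliminary report (6.2.2).
- Other SAE to METC: 15 days from the sponsor's first knowledge (6.2.2).
- Researchers to sponsor: no interval is given. The two are treated as one, so 0 days (assumption).

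**Reading (a): the clock starts with the sponsor.** Longest time from therapist awareness to METC = w + limit.
- Fatal or life-threatening: 7 + 7 = 14 days. Completed report: 7 + 7 + 8 = 22 days.
- Other SAEs: 7 + 15 = 22 days.
- The sponsor's own limits of 7 and 15 days are met in every case.

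**Reading (b): the clock starts with the therapist.** Days left when the researchers hear = limit − w.
- Fatal or life-threatening: 7 − 7 = 0 days.
- Other SAEs (for comparison; the text names the sponsor here): 15 − 7 = 8 days.

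If therapists learned of events evenly through the week, the mean wait would be 7/2 = 3.5 days. This is an illustration, not evidence of actual delay.

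**Do the other routes shorten the wait?**
- The self-injury questionnaire is given at assessments, which Table 1 places about three months or more apart. It is a self-report screener for non-suicidal self-injury, so it cannot report a death.
- The treating physician's contact (5.4) and the recording of adverse events (6.2.1) have no time limit.

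These routes may bring news sooner, but nothing requires them to.

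**Scope.** The weekly sentence covers SAEs needing medical care. Whether a death falls under it is unclear. If it does not, no therapist route is stated for deaths between assessments.

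**With prompt notice.** If therapists notify within d days, the longest times become d + 7 and d + 15. With d = 0 they are 7 and 15 days; with d = 1 they are 8 and 16.

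**The case against.** The strongest reply is that the plan does not contradict itself. A reader might infer that 14 days breaches the 7-day limit, or is twice that limit. The documents do not support this. The subject of the 7-day sentence is the sponsor, and the next sentence starts its clock at the sponsor's knowledge. Fourteen days counted from the therapist and 7 days counted from the sponsor are different clocks. A breach is at risk only if the therapist's knowledge counts, which the text leaves open. This part of the reply stands.

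A reader might also infer that the weekly meeting is the only channel. The text does not say so. It does not forbid earlier contact, and sections 5.4 and 6.2.1 offer other paths. That stands too, although none of those paths has a time limit.

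Nor is 14 days a ceiling from the event itself; it runs from therapist awareness. With an assumed further week until the next therapy session it would be 7 + 7 + 7 = 21 days. During the 6 to 9 month treatment pause in the trauma-only arms (Summary), the documents set no bound.

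Finally, the delay concerns notice to the committee, not patient care. The therapist already knows, section 3 allows crisis intervention, and section 5.4 keeps the treating physician as primary caregiver. No interim analysis or treatment estimate depends on these days. All of this limits the consequence. It does not explain why the most serious events should wait for a weekly meeting.

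**Conclusion.** The point holds as a weakness in the reporting route and an undefined start to one clock. It is not a breach of the stated limit. Followed as written, section 6.2.2 can add up to 7 days before the researchers know of an SAE. That makes at most 14 days from therapist awareness to the METC for fatal or life-threatening events and 22 days for others.

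These are worst cases. They need the longest wait for a consultation and full use of the sponsor's allowance. They also assume that no consultation is skipped, that nothing is lost between researchers and sponsor, and that the weekly sentence covers deaths. If the 7-day clock runs from the therapist, the wait can consume it entirely. The trial's estimates are unaffected. The gain is faster outside notice in a trial with no DSMB, which makes the change worth making.

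**What to change.** Amend section 6.2.2 in two places.

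1. Require therapists to notify the researchers of any SAE, explicitly including deaths and life-threatening events, as soon as they learn of it and within a short period that the protocol states. Keep the weekly consultation as a check that nothing was missed.
2. State whose first knowledge starts the 7-day period, consistent with the sponsor-based clock already given for the 15-day period. Moving both clocks to the therapist is not needed and would replace a rule the plan already states.

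The cost is a sentence or two, an instruction to therapists and a few extra messages. Design, sample size, analysis and treatment do not change.

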6.2.3. Suspected unexpected serious adverse reactions (SUSARs)

This part is not applicable to the presented study.

6.3 Annual safety report

Not applicable (no pharmacological or other agents involved in this study).

6.4 Follow-up of adverse events

All AEs will be followed until they have abated, or until a stable situation has been reached. Depending on the event, follow up may require additional tests or medical procedures as indicated, and/or referral to the general physician or a medical specialist. SAEs will be reported till the end of the study within the Netherlands, as defined in the protocol.

6.5 Data Safety Monitoring Board

It has been decided not to engage a Data Safety Monitoring Board in this study, no pharmacological or other agents are involved in this study. In addition, no interim analyses are planned. In the investigator's opinion, implementation of a DSMB will not have sufficient added value for the current study.

7. STATISTICAL ANALYSIS

Descriptive statistics of continuous outcomes will be presented by disorder category and include sample size, mean, median, standard deviation, minimum and maximum. For categorical outcomes, the number and percentage of subjects in each category will be presented by disorder category. Statistical analyses will be performed using SPSS for Windows (version 20) or in R (<https://www.r-project.org>).

7.1 Primary study parameters

For population description, the CAPS-5, M.I.N.I.-plus, SCID-5-PD, will be used in addition to the CTQ, LEC-5, DERS, ITQ, PAI-BOR, STAS, PSQI, DES-II, WAV, RSQ, CPI, BDI, AUDIT, WHODAS, EQ5D-5L, and Tic-P will be used (see Table 1). The subgroup of patients that underwent MRI will be compared to the rest of the group to test for pretreatment differences in PTSD severity and type/severity of PD.

The primary analysis in the RCTs will be improvement of PTSD symptoms at 3 time points. This primary analysis will include trauma symptom scores at T₀, T₂ and T₄ (CAPS-5, severity score) in a repeated measurements model, a linear mixed model for repeated measurements including at least time points, treatment group, the interaction between time point and treatment, sex, age and severity as fixed factors, baseline score as covariate and subject as random intercept factor. An cAR(1) structure will be used to model the residual covariance matrix. Responders will be defined as participants with a posttest score at least 1 SD below the pretest score (based on Jacobsen and Truax, 1991).

Secondary analyses will examine whether hormonal and epigenetic factors (5-HTTLPR, BDNF, cortisol/FKBP5-methylation, oxytocin/OXTR) mediate the treatment effects. Mediation analyses will include levels of the aforementioned variables on T₀ and T₂ to estimate the direct and indirect paths of casual treatment on the primary and secondary study parameters, through the proposed mediators.

For individual prediction analyses, machine learning techniques (in R: supervised and unsupervised techniques, e.g. the random forest model method) will be applied to separate treatment responders from non-responders based on clinical and neurobiological candidate predictors and in order to define the predictors

contributing most to classification accuracy, calculating sensitivity, specificity, and positive and negative likelihood ratios from the prediction model (Ball et al., 2014).

Candidate predictors that will be used are:

- Psychological factors: Cognitive factors (educational level/IQ, working memory, emotion regulation), Affective factors (hyperarousal: anger, sleep; hyperarousal: dissociation), and Relational factors (therapeutic alliance, attachment, social support);
- Neurobiological factors: Neural factors (smaller ACC and hippocampus volume, increased right amygdala and ventral ACC activity and de/increased dorsal ACC activity), and Hormonal/ epigenetic factors (5-HTTLPR, BDNF, cortisol/FKBP5-methylation, oxytocin/OXTR).

Questions that will be answered with machine learning in this study are:

1. Does brain activity predict treatment outcome for PTSD and PD (all treatment conditions together; N = 80)
2. Does brain activity predict treatment outcome for PTSD (EMDR and ImRs; N = 40)
3. Does brain activity predict treatment outcome for integrated PD/PTSD treatment (EMDR + DBT and ImRs + SFT, N = 40)
4. Data from the MRI at T2 can be used to predict relapse after treatment for all treatments together (N = 80 if all patients return for a second MRI) or for trauma treatment and integrated treatment separately (N = 40 for both).

fMRI data will be analysed with Statistical Parametric Mapping (SPM) software or FMRIB Software Library (FSL) to map connectivity in the brain. Standard group comparisons will be used to analyse structural and task-related (face recognition) fMRI. First, ANOVA analyses will be performed with patients vs. controls for baseline comparison. Second, full factorial analyses will be conducted in patients-only, with time (baseline vs. end of treatment) and condition (type of treatment) as factors to analyse the effect of treatment on (task-related) brain structure, connectivity and activity. Independent component analysis (ICA; FSL MELODIC) and dual regression analyses will be used to study changes in functional connectivity of brain networks (with a focus on the salience

network, negative affect network, ventral and cognitive control network). Brain areas that fluctuate simultaneously over time in blood-oxygen level dependent (BOLD; proxy for brain activity) response are automatically assigned to a component per subject. After filtering and preprocessing of the components (e.g. components that are caused by movement or scanning artefacts), these components are averaged across groups. Through non-parametric permutation testing (FSL randomise) we compare functional connectivity of these networks between intervention groups and over time (T₀ to T₂). For the whole-brain network analyses, the structural MRI will be parcellated into 92 regions of interest (ROIs), based on the Automated Anatomical Labeling (AAL) atlas. These parcellations will be transformed to resting-state fMRI and time series are extracted for each ROI and correlated to get a whole-brain connectivity matrix per subject. The brain connectivity toolbox (BCT) will be used to calculate network topological indices (e.g. modularity, betweenness centrality, clustering coefficient and efficiency) from these matrices. Network topological indices narrow down the large amount of information from the brain scans to a few neurobiologically meaningful measures (Rubinov & Sporns, 2010). A more detailed description of these topological measures can be found in Bullmore and Sporns (2009). These measures will be calculated for every condition and compared through permutation-testing.

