treatment (1.0), the number of persons needed to include is 50 persons per condition to reach for 80% power. Expecting a dropout rate of 25%, we will include 63 persons per arm, for 4 arms a total of 252 adult patients with PTSD and - at least 4 - PD symptoms. Of these patients, 80 next to 40 healthy matched controls will be asked for additional MRI research before and after treatment. In total, 292 persons will be included in this study.

Intervention: In patients with PTSD and BPD: EMDR (3-6 months plus 6-9 months treatment pause) compared to integrated DBT-EMDR (12 months); in patients with PTSD and CPD: ImRs (3-6 months plus 6-9 months treatment pause) compared to integrated ImRs-SFT (12 months).

Main study parameters/endpoints: Primary outcome measure is PTSD symptom severity after 12 months. Secondary outcome measures are PD symptoms (SCID-5-PD), disability (WHODAS), quality of life (EQ-5D-5L) and health costs (Tic-P). At baseline (T₀) and after 12 months (T₄) clinical interviews (CAPS-5, SCID-5-PD dimensional score) and self-rating scales (PCL-5) will be used. After 3 (T₁), 6 (T₂), 9 (T₃), and 18 months (follow-up), questionnaires only will be used. At baseline, candidate predictors will be measured including above mentioned cognitive, affective, relational factors, and hormonal and epigenetic factors. In a subgroup, structural and functional MRI, with resting-state and an emotion processing (face recognition) will be performed.

Nature and extent of the burden and risks associated with participation and benefits:

The burden and risks associated with participation in this study is reasonable. All patients will receive psychotherapy, which is considered to be the most effective treatment for PTSD and PD. There is evidence that all four conditions are therapeutic in patients with PTSD and PD and no evidence yet what condition is more effective. Total time of the six measurements is approximately 5 hours per patient for interviews and 5 hours for questionnaires (see table 3), which are partly part of the routine outcome measurements (ROM). Questionnaires can be filled in at home. On the one hand, extensive clinical interviews and self-rating scales can be felt as disturbing because of fatigue, taken time and emotional burden. On the other hand, patients may feel well recognized by the time taken by specialized clinicians for them. Assessors will be well-trained and work in close

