4.4 Sample size calculation

A power calculation was made based on Twisk (2007). We assume that PTSD treatment (EMDR or ImRs) have a small effect size (< 0.5) in the complex patient group with PTSD and comorbid

CPD/BPD, while the integrated treatment will show double effect sizes (1.0) (Harned et al., 2014). With a minimal clinical relevant difference of a 0.5SD on the CAPS-5, and the assumptions of a SD of 20.0, an intra-person correlation coefficient of 0.7, 5 follow-up measurements, the needed number to include is 50 persons per condition to reach for 80% power. Expecting a drop-out rate of 25%, we will include 63 persons per arm, or for 4 arms in total 252 persons.

In 2016, approximately 950 new patients were referred to the SC (Amstelveen). From these patients, ca. 450 had PTSD. From these PTSD patients, 168 had a comorbid PD and 188 more were not assessed for personality traits (“Uitgestelde diagnose”). We expect that introducing the assessment of axis II assessments with this study will result in an estimated 300 patients with PTSD and PD per year, and after 33% refusals or exclusions, in an estimated 200 patients possible to include per year. To be sure to include enough patients, we will need to include more patients from another site of the

Sinai Center, i.e. Amersfoort (400 patients, from which 216 PTSD patients, from which an estimated 100 PTSD + PD patients), and extend the inclusion period.

From these 252 patients, 80 will be asked for additional MRI, next to 40 healthy controls (Total sample size = 292). An estimated 40 patients will be available for a second MRI after 6 months (total of 160 scan sessions).

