5. METHODS

5.1 Study parameters/endpoints

5.1.1 Primary outcome parameters

○ Severity of PTSD (DSM-5) as measured with:

- CAPS-5 (Clinician Administered PTSD Scale, Weathers et al., 2014, Boeschoten et al., 2014). The first psychometric evaluation of the CAPS-5 showed good reliability, convergent and divergent validity (Weathers et al., 2017). Severity of PTSD is measured on a continuous scale on the CAPS-5. All 20 symptoms of PTSD from the DSM-5 are assigned a severity score of 0-4. These 20 scores are then summed to calculate total PTSD symptom severity.

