7.2 Secondary study parameters

Secondary study parameters are quality of life with WHODAS, EQ-5D-5L, and health care consumption with Tic-P. The secondary analyses on these continuous measures will be similar to the primary analyses.

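### The primary mixed model uses the T0 CAPS-5 as both outcome row and baseline covariate and names no primary contrast, so its standard errors are unreliable (about 10% type I error for the adjusted 12-month difference)

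*Combined protocol and SAP*

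**What the plan says.** Section 7.1 introduces the analysis with "The primary analysis in the RCTs will be improvement of PTSD symptoms at 3 time points" and continues: "This primary analysis will include trauma symptom scores at T₀, T₂ and T₄ (CAPS-5, severity score) in a repeated measurements model". The same sentence gives the fixed part, "including at least time points, treatment group, the interaction between time point and treatment, sex, age and severity as fixed factors, baseline score as covariate", with a random intercept per subject. On the covariance it says only "An cAR(1) structure will be used to model the residual covariance matrix".

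No coefficient or contrast is named as the primary test. The Summary fixes the time: "Primary outcome measure is PTSD symptom severity after 12 months". The hypotheses in section 1 and the objectives in section 2 also speak of response rate, and the research questions in section 5.3 ask about 12 months for A1 but about 6, 12 and 18 months for A2. No significance level or sidedness is stated anywhere.

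Section 7.2 extends the approach: "The secondary analyses on these continuous measures will be similar to the primary analyses". Section 7.3 does the same for the remaining outcomes.

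**The concern.** A baseline measurement can be an outcome in a longitudinal model or a covariate in it. As both, it creates rows in which the response equals a predictor. Those rows have almost no residual, whereas T2 and T4 have a large one. A covariance model with one residual variance averages the two, and the average is wrong for every visit.

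The effect on a test then depends on which contrast is reported and on how the correlation between visits behaves. Because the plan names no contrast, the analyst could choose, after seeing the data, among tests whose error rates differ about threefold. This is the primary analysis of both RCTs, and sections 7.2 and 7.3 carry it to the other outcomes.

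**Working it through.** **Inputs.** Section 4.4: SD 20, difference 0.5 SD (10 points), 80% power, 50 per arm, 25% dropout (63 per arm), and "an intra-person correlation coefficient of 0.7, 5 follow-up measurements". Assumed: two-sided 5%, cAR(1) as homogeneous equally spaced AR(1), dropout of 12.5% by T2 and 25% by T4.

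**1. The plan's own figure.** The documents give no type I error to reproduce, only the sample size. The usual repeated-measures formula gives

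n = 2(1.96 + 0.842)² × 20² × [1 + (5 − 1) × 0.7] / (5 × 10²) = 47.7, so 48 per arm against the stated 50.

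One-sided 5% would give 37.6. The stated size therefore fits a two-sided 5% test with equal correlation 0.7, and both are used below.

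**2. Adjusted difference at T4** (unit SDs, complete data, no treatment effect).
- One baseline slope for three rows: s = (1 + 0.7 + 0.7)/3 = 0.80 (REML fits give 0.81).
- Residual variance at T0: (1 − 0.80)² = 0.04.
- At T2 and T4: 1 + 0.64 − 2 × 0.7 × 0.80 = 0.52.
- Pooled: (0.04 + 0.52 + 0.52)/3 = 0.36.
- Standard error at 50 per arm: the model gives √(2 × 0.36/50) = 0.120; the true value is √(2 × 0.52/50) = 0.144. Ratio 0.832, about 17% too small.
- Type I error: 2[1 − Φ(1.96 × 0.832)] = 10.3%.

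With dropout the rows weigh 1, 0.875 and 0.75 (total 2.625). Then s = (1 + 0.7 × 1.625)/2.625 = 0.814, the variances are 0.034 and 0.523, pooled 0.337, ratio 0.803, and the error is 11.6%.

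With serial decay (T0-T4 correlation 0.49), s = 0.73, the variances are 0.073, 0.511 and 0.818, pooled 0.467, ratio 0.756, and the error is about 14%. With decay and dropout, s = 0.754, the variances are 0.060, 0.513 and 0.830, pooled 0.431, ratio 0.721, and the error is about 16%.

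**3. T4-T0 interaction.** The baseline term cancels from the estimate but not from its standard error. Under equal correlation the true variance of the change is 2(1 − 0.7) = 0.60. The residual covariances are 0.2 × (0.7 − 0.8) = −0.02 for T0 with either later visit, and 0.7 − 2 × 0.8 × 0.7 + 0.64 = 0.22 for T2 with T4. Matching an AR(1) to their lag-1 average gives φ = 0.10/0.36 = 0.28 and an implied T0-T4 covariance of 0.36 × 0.28² = 0.028. The model variance is 2(0.36 − 0.028) = 0.664, which is too large, and the error is 2[1 − Φ(1.96 × √(0.664/0.60))] = 3.9%.

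Under the serial decay above, the true variance is 2(1 − 0.49) = 1.02. The residual covariances are −0.008 and 0.364, so φ = 0.178/0.467 = 0.38. The model variance is 2(0.467 − 0.068) = 0.80, which is too small, and the error is about 8%.

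**4. Simulation.** REML fits of the stated model (random intercept plus AR(1)), mostly 2000 null trials per scenario; Monte Carlo SE is about 0.7 points at 10% and 0.5 at 5%. Most runs included sex and age as noise. Baseline SD was 0.7 to 1.0 times the later SDs. Severity was left out because it is undefined. Decay means a T0-T4 correlation of 0.55 or 0.49 with 0.7 between neighbouring visits.

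| Test | Equal 0.7, complete | Equal 0.7, dropout | Decay, complete |
|---|---|---|---|
| Adjusted T4 difference | 9.2-11.8% | 11.5-11.9% | 12.1-14.2% |
| T4-T0 interaction | 2.9-4.1% | 4.4-5.6% | 6.2-8.8% |
| Joint time-by-treatment (2 df) | 4.8-6.3% | 7.0-8.0% | 5.8-7.6% |
| Treatment effect averaged over visits | 4.7-6.7% | 6.8-7.4% | 3.5-4.8% |
| T0 as covariate only, T4 difference | 4.2-5.6% | 4.9-5.2% | 6.5-8.7% |
| Repaired model (see the fix), T4 difference | 4.8-5.8% | 4.9-5.4% | 4.8-5.6% |

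At equal correlations of 0.5 and 0.3 with equal visit SDs and complete data (both correlations assumed), the adjusted T4 difference gives 9.1-9.6% and 9.3-9.8%.

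**The case against.** The strongest reply is that the documents never say the adjusted T4 difference will be tested. Section 7.1 speaks of improvement and lists the time-by-treatment interaction, which points at least as naturally to change from T0, and that test is conservative under equal correlation. This stands. A reader might infer that the planned primary test has twice its nominal error; the documents do not support that, because they name no test. The opposite inference, that only the adjusted T4 difference is affected, also fails: the interaction reaches 6-9% under decay, and the joint and averaged tests about 7-8% with dropout.

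Second, T0 may have been meant as covariate only. The sentence can bear that, and most of the fault then goes. It fits poorly with the explicit list of three visits and with an analysis described as covering three time points. Under decay an AR(1) model still gives 6.5-8.7%.

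Third, cAR(1) is an unexplained label. Homogeneous variance is one reading of it, and the pooling depends on that reading. T2 is also timed to the end of trauma treatment, so spacing may vary. Both are conditions on the figures; neither supplies the missing specification.

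Two further inferences should be resisted. The word severity could mean the baseline CAPS-5 again, since section 5.1.1 says "Severity of PTSD is measured on a continuous scale on the CAPS-5", but section 7.1 also uses the word for personality disorder, and an identical score entered linearly twice would be redundant and leave the treatment test unchanged. Nor is power lost in a way that matters: in the runs made, the interaction and joint tests roughly keep the planned 80% or more.

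**Conclusion.** The concern holds as a fault of specification. As written, T0 is both outcome and covariate, no primary contrast is named, and the model's standard errors can be wrong in either direction depending on the contrast and the correlation pattern. For the adjusted 12-month difference, the contrast closest to the Summary's primary outcome, the type I error is about 10% under equal correlation 0.7, about 9-12% across visit SDs and dropout, and about 12-16% if correlation decays. These figures rest on T0 being an outcome row, a homogeneous AR(1), an assumed two-sided 5% level, and that contrast being tested. It should be corrected before analysis, because the error rate of the primary test cannot be stated from the plan.

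**What to change.** Rewrite the primary model in section 7.1 in one of two ways:
- CAPS-5 at T2 and T4 as outcome rows and baseline CAPS-5 as covariate, preferably with a baseline-by-time term and an unstructured residual covariance; or
- T0, T2 and T4 as outcomes with a common baseline mean in both arms and no baseline covariate.

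Name the adjusted treatment difference at T4 as the primary contrast in both RCTs, and state alpha and sidedness. Apply the same correction to the analyses that sections 7.2 and 7.3 model on the primary one. As a minor clarification, say what severity means as a fixed factor.

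The cost is wording only, with no new data or visits. The first option gave 4.8-5.8% error in every scenario run. Its power for 0.5 SD at T4 was 92-93%, against 86-90% for the T4-T0 interaction and 80-85% for the joint test; these power figures assume a 0.25 SD effect at T2, which the documents do not give.
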